**B. OVERVIEW AND SPECIFIC AIMS**

The overarching goal of this research is to increase retention on antiretroviral therapy (ART) among people living with HIV (PLWH) in sub-Saharan Africa, the region most affected by the global HIV pandemic. With the goal of ending the pandemic, the UNAIDS “90-90-90” targets for 2020 are that 90% of all PLWH know their HIV status, 90% of people with diagnosed HIV infection receive sustained ART, and 90% of all people receiving ART achieve viral suppression. While Rwanda is very close to achieving these targets, certain groups such as men and younger PLWH are at higher risk of poorer outcomes. Reducing barriers to initiating and adhering to therapy is thus paramount to ensuring all PLWH in Rwanda succeed in HIV therapy.

In the qualitative work that we have conducted as part of the current research grant, patients reported multiple barriers to attending appointments including structural issues (transportation cost, distance to the health center, long waiting times) and facing stigma while traveling to and while at the

health center. Reducing the frequency of medical appointments for patients who are clinically stable in care could potentially reduce the burden faced by these patients. Indeed, the WHO recommends such an approach to address the specific needs of different groups of PLWH and reduce burden on the health system. While WHO guidelines define “clinically stable” patients as those on ART for 1 year with 2 consecutive viral loads, research studies as well as HIV programs in sub-Saharan Africa have defined “clinically stable” PLWH as those on ART for shorter intervals (i.e. 6 months after diagnosis) and/or with only 1 suppressed viral load. *However, to date, no studies to our knowledge have compared how a shorter time on ART or only 1 viral load measurement compare to the current WHO guidelines.*

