The objectives of this study are to thus pilot test the effect of reducing time to spaced-out appointments from 18 to 6 months for newly-diagnosed PLWH in Rwanda. This is a critical time to conduct this work, as most African countries have adopted differentiated care models. Rwanda, where this study is based, was among the first countries to implement Treat All as a national policy and remains a leader in HIV outcomes. To better understand the effects of early spaced-out appointments as well as the degree of viral load monitoring needed to determine stability, we will conduct a 3-arm pilot intervention study. We will enroll 90 patients: 30 will be randomized to 6-month advancement to spaced out appointments after 1 suppressed viral load (at 5 months after enrollment) (“*Early 1*”); 30 will be randomized to 6-month advancement to spaced-out appointments after 2 suppressed viral loads (at 3- and 5-months after enrollment) (“*Early 2*”); and 30 will be randomized to continue in usual care (“*Usual care*”). We will compare the study arms with respect to viral suppression at 12 months after enrollment (primary outcome) and appointment/ pharmacy adherence (secondary outcome). We hypothesize that reducing the time to the “clinically stable” phase to 6 months will be feasible, acceptable, not inferior to usual care with respect to viral suppression or adherence, and will be cost-effective. The specific aims of this study are:

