### Study participants, recruitment and enrollment

- **Inclusion/exclusion criteria:** *Inclusion* criteria for the study are: 1)  $\geq 15$  years; 2) newly-diagnosed with HIV; 3) enrolled in care at study health facility; 4) initiated ART. *Exclusion criteria* are: 1) planning on moving away from health center/Kigali in the next 12 months; 2) unable to provide informed consent; 3) enrolled in care while pregnant; 4) co-infected with tuberculosis; 5) concurrent known mental health or substance use disorder.
- **Recruitment:** A study research assistant will work with staff at the health facility to identify persons who are newly-diagnosed with HIV and may be eligible for the study. We will have clinic nurses inform potentially eligible patients about the study during appointments and provide study contact information. We will also put up posters in health facilities with study information.
- **Screening procedures:** The research assistant will meet with interested participants to describe the study and offer enrollment during a follow-up appointment after their enrollment into care. Patients who are interested in participating in the study, who meet criteria and who provide written informed consent will be enrolled in the study and be randomized to either the intervention arms or the standard of care arm.
- **Randomization:** randomization will be stratified by age ( $<24$  vs  $\geq 24$ ) and by clinic and occur in blocks of 4-8, with 1:1:1 allocation of the three study arms.

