### Main outcome variables

- **Preliminary efficacy:** *Primary outcome* is viral suppression (defined as viral load <200) at 12 months (yes/no). *Secondary outcome* is appointment and pharmacy adherence (attended all appointments/missed ≥1 appointment).
- **Feasibility/acceptability:** patient satisfaction with appointment schedule, health worker satisfaction with appointment schedule, patient experiences of stigma
- **Cost:** we will collect data on patient-level costs borne by patient or relatives of the patient towards their care (i.e. transportation to clinic, missed days of work). To ascertain the cost to the health facility, we will estimate fixed (i.e. equipment, human resources) and variable (i.e. type and number of visits, laboratory tests, inpatient care) costs to care.

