### Data analysis

- **Assessment of randomization:** we will compare all covariates between the 3 study arms, using t-tests (or non-parametric tests) for continuous variables and chi-square (or Fisher tests) for categorical variables.
- **Preliminary efficacy:** We hypothesize that viral suppression and appointment/pharmacy adherence will be similar across the 3 study arms. We will first compare proportions of patients achieving viral suppression and attending all appointment/pharmacy visits using chi-square tests. We will use generalized estimating equations to estimate risk differences, risk ratios and associated 95% confidence interval for the effect of each intervention arm compared to the control. The non-inferiority limit will be set at 10%. Because of the small number of participants we will be able to enroll in this pilot study, it may not be sufficiently powered to detect a statistically significant differences in outcomes. However, the findings and the effect size obtained from this study will provide key results on intervention feasibility and guide a future, larger study to test intervention efficacy.
- **Cost analysis:** We hypothesize that the intervention arms will result in reduced patient-level and health-center costs. Outcomes will include: (a) annual cost per patient in each cohort/arm (per patient year cost); and (b) cost-effectiveness of the intervention arms compared with usual care.

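### The GEE 95% CI for one yes/no outcome in 30 patients per arm is by default a Wald interval, which declares non-inferiority too easily when suppression is high; use a score or Newcombe interval

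*Combined protocol and SAP*

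**What the plan says.** The Preliminary efficacy item under Data analysis states: "We will use generalized estimating equations to estimate risk differences, risk ratios and associated 95% confidence interval" for each intervention arm against usual care. It then adds "The non-inferiority limit will be set at 10" percent. It does not name the cluster unit, link, working correlation, covariates, type of standard error, any small-sample correction, or what happens if an arm has no failures. Fisher tests appear only in the baseline comparison of arms.

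Main outcome variables defines the primary outcome as "viral suppression (defined as viral load <200) at 12 months (yes/no"). The adherence outcome is also one binary value per person: "attended all appointments/missed ≥1 appointment".

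Section B gives the size: "We will enroll 90 patients: 30 will be randomized to 6-month advancement to spaced out appointments after 1 suppressed viral load", with 30 in each of the other two arms. No suppression rate is assumed anywhere. The only guide is the 90-90-90 discussion in Section B, which says "Rwanda is very close to achieving these targets". On the design, "randomization will be stratified by age" and by clinic.

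**The concern.** GEE is built for correlated observations. Here each person contributes one value, so there is no within-person correlation to model. With the person as cluster, the usual robust standard error reduces to the unpooled Wald formula. That formula is known to be too small when proportions are near 1 and samples are small, and it is zero when nobody fails.

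The error runs in the unsafe direction for non-inferiority: an interval that is too narrow clears the 10% limit too often. The protocol states a non-inferiority hypothesis, sets a limit, and says the results will inform national policy and a larger study. The choice of interval can therefore decide the stated conclusion.

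**Working it through.** **Inputs.** 30 per arm (Section B); one binary outcome per person (Main outcome variables); 95% CI and 10% limit (Data analysis). Assumptions: the limit is 10 percentage points on the risk difference; the interval is two-sided, so the nominal one-sided error is 2.5%; control suppression ranges over 85% to 97%. The plan gives no power or error figure to reproduce.

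**Step 1: the default GEE interval is Wald.** With an identity link, an arm indicator, independence and each person as a cluster, the robust variance is

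SE² = pT(1-pT)/nT + pC(1-pC)/nC.

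For 29/30 v 29/30: SE = sqrt(2 × 0.9667 × 0.0333 / 30) = 0.04635, and the lower limit is 0 - 1.96 × 0.04635 = -0.0908. A fitted GEE gives the same SE and limit. At 28/30 v 28/30 both SEs are 0.06441. A bias-reduced sandwich at 29 v 29 gives SE 0.04795 and a lower limit of -9.4 points, so the verdict does not change. At 30/30 v 30/30 the GEE robust SE is 0 with a binomial or Poisson family, and the fit fails with a Gaussian family. The robust SE of the log risk ratio is also 0 there.

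**Step 2: alternatives on the same tables.** Newcombe's lower limit is d - sqrt[(pT - LT)² + (UC - pC)²], where L and U are Wilson limits. For 30/30, L = 30/(30 + 1.96²) = 0.8865 and U = 1, so the lower limit for 30/30 v 30/30 is -(1 - 0.8865) = -11.4 points (-0.1135 before rounding).

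| Intervention v control | Wald/GEE | Newcombe | Miettinen-Nurminen |
|---|---|---|---|
| 30/30 v 30/30 | 0.0 | -11.4 | -11.5 |
| 29/30 v 29/30 | -9.1 | -13.6 | -13.9 |
| 29/30 v 30/30 | -9.8 | -16.7 | -16.8 |

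All three are non-inferior by Wald and not by either alternative. With 24 or more suppressed per arm, the methods also disagree at 29 v 28 and 28 v 26, again with only Wald declaring non-inferiority.

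**Step 3: exact error rates.** Sum the binomial probabilities of all 31 × 31 tables whose lower limit exceeds -0.10, with pT = pC - 0.10 (false non-inferiority).

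| Control suppression | Wald | Newcombe | Miettinen-Nurminen |
|---|---|---|---|
| 85% | 3.0% | 2.3% | 2.2% |
| 90% | 3.2% | 2.0% | 2.0% |
| 95% | 5.5% | 1.6% | 1.6% |
| 97% | 8.6% | 1.4% | 1.4% |

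With 25 to 29 evaluable per arm, Wald gives 3.4-4.3% at 90% and 4.2-5.7% at 95%; the score interval gives 1.7-2.3%.

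**Step 4: equal arms.** With pT = pC, non-inferiority is declared in 29% (Wald) v 18% (score) of comparisons at 90%, and 57% v 24% at 95%. The choice of interval thus decides about 10% of comparisons at 90% and 33% at 95%.

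**Step 5: stratification.** Simulation used 100,000 two-arm comparisons of 60 patients, four equal clinics, an assumed 25% under 24, and an age difference of 0 or 5 points. At control rates of 85-95%, a score interval with Mantel-Haenszel weights gave 1.5-2.4% false non-inferiority. Unstratified score gave 1.7-2.3% and Wald 3.0-5.4%.

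**Step 6: if clinic were the cluster.** The plan does not say this; Study setting names four sites. An uncorrected sandwich on four equal clinics (40,000 simulations) gave 10.2%, 10.9% and 13.1% at 85%, 90% and 95%.

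**The case against.** **The Wald interval is inferred.** The plan names GEE and leaves its settings open, so one could ask only that they be stated. That is fair as far as it goes. But the usual settings give Wald, and the bias-reduced sandwich checked above leaves the 29 v 29 and 30 v 30 verdicts unchanged, so naming the settings would not be enough.

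**The excess is small at the documents' only anchor.** At 90% suppression Wald is 0.7 points over nominal and the score interval 0.5 points under. The larger figures need 95% or more, which the plan never states. The 90% is also a target for people on ART generally, while this trial enrols newly diagnosed patients. Counting missing viral loads as failures would lower the rate further. This stands as a limit on the size of the problem. Against it, with 25 to 29 evaluable per arm Wald is 3.4-4.3% even at 90%.

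**The zero-width table is rare.** With both arms truly at 95% it occurs with probability 0.95^60, about 4.6%, and an analyst would notice it. True; the 29/30 tables matter more, and nothing in their output would look odd.

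**It is a pilot, with an admitted lack of power.** That caveat warns of missing a difference. It does not warn of declaring non-inferiority too easily. No explicit decision rule is written, but a hypothesis and a limit are.

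**Adherence is different.** At control rates of 50-70%, Wald gives 2.6% and score 2.3-2.6%, practically the same. Using one method for both outcomes is then a matter of consistency.

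**Conclusion.** The concern holds. In its default form the planned interval is the unpooled Wald interval, and at 30 per arm it exceeds the nominal 2.5% false non-inferiority rate across the range examined: slightly at 85-90% control suppression (3.0-3.2%), about twofold at 95% (5.5%) and more than threefold at 97% (8.6%). Score and Newcombe intervals stay below 2.5% at 30 per arm over the same range. This rests on a margin of 10 percentage points, a two-sided 95% interval, the person as cluster and an assumed suppression rate. The excess varies with the number evaluable but persists at 25 to 29 per arm.

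**What to change.** For 12-month suppression, replace the GEE interval with a Miettinen-Nurminen (score) or Newcombe 95% CI for the risk difference, and compare its lower limit with -10 percentage points.

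- Preferably stratify the score interval by the randomization factors with Mantel-Haenszel weights. This is for consistency with the design; omitting the strata did not inflate error in the check. Prespecify a merging rule, for example: if any age-by-clinic cell has no patient in one of the two compared arms, stratify by age group only.
- Do not use a sandwich variance clustered on clinic.
- Use the same interval for the adherence outcome.
- If the risk ratio is kept, give it a score interval too, since its GEE standard error also collapses when nobody fails.

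The cost is SAP wording and standard software, with no extra patients, visits or data. The downside is wider intervals. Even 30/30 v 30/30 would not meet the limit, and with 95% suppression in both arms non-inferiority would be declared in 24% of comparisons instead of 57%. That reflects what 30 per arm can show, and it supports presenting the interval mainly as an estimate to guide the larger study.

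### The 10% non-inferiority limit has no stated scale and is judged by equality tests and an unspecified GEE interval; in its simplest form that interval is mildly to clearly anti-conservative with 30 per arm

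*Combined protocol and SAP*

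**What the plan says.** The Overview (section A), the specific aims (section B, including Aim 1a) and Potential risks (section D) all state a non-inferiority hypothesis: the early arms will be no worse than usual care on viral suppression or adherence.

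Only the Preliminary efficacy item under Data analysis says how this will be judged. It makes five statements:
- It recasts the hypothesis: "We hypothesize that viral suppression and appointment/pharmacy adherence will be similar across the 3 study arms".
- The first step is a test of equality: "We will first compare proportions of patients achieving viral suppression and attending all appointment/pharmacy visits using chi-square tests".
- The second step, for each early arm against control, is "generalized estimating equations to estimate risk differences, risk ratios and associated 95% confidence interval".
- The margin is one sentence: "The non-inferiority limit will be set at 10" per cent.
- It gives a caution on power: "it may not be sufficiently powered to detect a statistically significant differences in outcomes".

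Main outcome variables defines the primary outcome as a single yes/no per patient (viral load below 200 at 12 months) and adherence as all appointments attended or at least one missed. Randomization is stratified by age group "and by clinic and occur in blocks of 4-8, with 1:1:1 allocation of the three study arms". No section names the GEE cluster unit, link or small-sample correction, the scale of the 10%, or whether the limit also covers adherence.

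**The concern.** A chi-square test of equality uses neither the direction nor the margin of the hypothesis. In a small trial it is usually non-significant, and with the hypothesis worded as similarity, a non-significant result invites the conclusion that the arms are alike.

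The margin must therefore be judged from the GEE interval, and several different intervals fit the plan's words. The simplest is the Wald interval, which is known to be too narrow when proportions are near 100% and groups are small. High suppression is plausible here: section B says Rwanda is very close to its targets, one of which is 90% suppression among people on ART.

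The Overview in section C says the findings will inform national policy on differentiated care. Whether an early arm is reported as non-inferior should not turn on an interval or scale chosen after the data are seen.

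**Working it through.** **Inputs.** From the documents: 30 per arm, a 10% limit, 95% intervals, one binary result per patient. Assumed, because no expected rate is given: control suppression of 80%, 90% or 95%; 30 evaluable per arm, with 25–27 as a check; 10% read as percentage points unless stated. The plan gives no sample-size or power figure to reproduce.

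**1. Chi-square step.** Suppose usual care is 27/30 and an early arm 24/30, an observed loss equal to the margin. The pooled proportion is 51/60 = 0.85, so z = 0.10 / √(0.85 × 0.15 × 2/30) = 1.08, chi-square = 1.18 and p = 0.28. A non-significant result says nothing about the margin.

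**2. What GEE gives.** With one record per patient, arm as the only covariate, identity link and robust variance, the GEE standard error is √[p₁(1−p₁)/n + p₀(1−p₀)/n], the unpooled Wald formula. A fitted GEE agrees: at 28/30 vs 29/30 both give 0.0561.

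**3. Near-ceiling results (early vs usual care).**
- *29/30 vs 30/30.* The difference is −0.0333 and SE = √(0.9667 × 0.0333/30) = 0.0328. The Wald lower limit is −0.0333 − 1.96 × 0.0328 = −9.8 points, which meets −10. Newcombe uses the Wilson lower limit for 29/30, 0.8333: −0.0333 − (0.9667 − 0.8333) = −16.7 points, which does not.
- *30/30 vs 30/30.* The Wald SE is 0, so the interval has zero width. Newcombe runs from −11.4 to +11.4 points.

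**4. Long-run error.** Exact enumeration of all 31 × 31 outcomes gives the chance that the lower limit exceeds −10 points:

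| Control rate | True 10-point loss: Wald | True 10-point loss: Newcombe | Equal arms: Wald | Equal arms: Newcombe |
|---|---|---|---|---|
| 80% | 2.9% | 2.6% | 17% | 15% |
| 90% | 3.2% | 2.0% | 29% | 18% |
| 95% | 5.5% | 1.6% | 57% | 24% |

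The nominal error is 2.5%. With 25–27 evaluable per arm, the Wald error is 3.6–4.3% at 90% and 4.2–5.0% at 95%. Miettinen-Nurminen with 30 per arm gives 2.4%, 2.0% and 1.6%.

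**5. If GEE clustered on clinic.** Central Africa-IEDEA names three participating sites; Study setting adds a fourth. Simulation with uncorrected robust variance and no true clinic effect gives errors of 10.5%, 11.7% and 13.5% at 80%, 90% and 95% with four near-equal clinics, and 13.9%, 15.6% and 17.4% with three clinics of ten per arm. With three equal clinics, some lower limits fall exactly on −10 points. Excluding those ties gives about 13.7%, 14.6% and 15.7%.

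**6. Scale.** A relative 10% equals 8.0, 9.0 or 9.5 points at control rates of 80%, 90% or 95%. At 26/30 vs 23/30 the Wald lower limit for the difference is −9.4 points (met). The ratio limit is exp[ln(26/23) − 1.96 × √(1/26 − 1/30 + 1/23 − 1/30)] = 0.887, below 0.90 (not met). With equal arms the two readings disagree in 4.2% of datasets at 80%, 0.3% at 90% and almost none at 95%.

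**The case against.** The strongest reply is that this is a pilot: efficacy is labelled preliminary, low power is admitted, and the effect size is meant to guide a larger study. That limits the severity. It does not say how a limit the plan chose to set will be read.

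Several stronger readings are tempting, and the documents do not support them:
- *The GEE interval is unreliable in general.* At 90%, the only benchmark in the documents, the patient-level error is 3.2% against 2.5%. The clear failure needs an assumed 95%.
- *GEE here can only be the Wald interval.* That holds for one record per patient in an arm-only model. Viral load is scheduled more than once per patient and adherence is collected at several visits, so a repeated-measures or covariate-adjusted model is also open.
- *The trial will have error rates of 11–18%.* No section says GEE clusters on clinic; clinic appears only as a randomization stratum. The figure shows what the wording allows.
- *The choice of interval will often change the answer.* With equal arms, Wald and Newcombe disagree on the limit in 33% of datasets only at 95% with exactly 30 per arm. This falls to about 16–17% with 25–27 evaluable, and is about 10% at 90%. The 29/30 vs 30/30 example is equally fragile: at 28/29 vs 29/29 the Wald limit is −10.1 points and no longer meets.
- *The unstated scale threatens the primary result.* It hardly matters at high suppression. It could matter more for all-or-none adherence, whose rate is unknown.
- *The unstated bound and crossing rule are serious gaps.* For a favourable outcome the lower limit is the only sensible bound, and an interval that crosses the margin has by convention not shown non-inferiority.

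**Conclusion.** The point holds in a limited form. The plan judges a non-inferiority hypothesis first by tests of equality, then by an interval whose cluster unit is unstated, against a limit whose scale is unstated. The simplest reading for the primary outcome is mildly anti-conservative at 90% control suppression (3.2%; 3.6–4.3% with 25–27 evaluable) and clearly so at 95% (5.5%; 4.2–5.0%), against 2.5%. It breaks down when both arms are fully suppressed. The wording also leaves open a clinic-clustered version that would be much worse.

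All sizes rest on assumed control rates, independent patients and the analysis models described above. Confidence is high that the scale and cluster unit are missing, and lower that the interval would mislead in practice. Severity is minor to moderate.

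**What to change.** In the Preliminary efficacy item of Data analysis:
1. Make the chi-square tests descriptive.
2. State the reading of the limit, for example: *for each early arm, the lower limit of the two-sided 95% Newcombe (or Miettinen-Nurminen) confidence interval for the risk difference in 12-month suppression, early arm minus usual care, is compared with −10 percentage points; an interval that crosses this limit is reported as inconclusive, not as similar.* Name one of the two methods in advance.
3. Say whether the limit also covers adherence and, if so, on which scale.
4. Keep the GEE risk differences and ratios as supportive, with the patient and not the clinic as the cluster unit.

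Stratifying the interval by age group and clinic is optional.

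This costs a few sentences and no patients. The price is a lower chance of meeting the limit when arms are truly equal: about 18% instead of 29% at 90%, and 24% instead of 57% at 95%, with 30 per arm. If usual care is 30/30, no early-arm result can meet the limit, because even 30/30 gives a Newcombe lower limit of −11.4 points. The chance of that is 0.90³⁰ = 4% at 90% and 0.95³⁰ = 21% at 95%. Both costs are acceptable in a pilot that already admits low power.

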### Research visits

- All participants will have research visits at baseline (study enrollment, which will occur in the first month after enrollment), month #6 after enrolling in HIV care, and month #12 after enrollment. Participants will undergo interviews at all study visits, and will undergo follow-up viral load testing

at 12 months. Participants will be compensated 8,000 Rwandan francs (RWF), approximately \$8 USD, at each visit.

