**Table 2. Data collection**

Measure	Instrument/source	Research visit		
		Baseline	6 mo	12 mo
REDCAP Questionnaire				
Socio-demographic information	Sociodemographic form	x		
Quality of life	EQ-5D 	x	x	x
Patient satisfaction with care	Patient satisfaction with care 	x	x	x
Other healthcare utilization	Other healthcare utilization form	x	x	x
Medication adherence	7-day medication adherence recall		x	x
HIV stigma - anticipated	Earnshaw & Chadoor 	x	x	x
HIV stigma - experienced	HASI-P 	x	x	x
Patient costs/expenditures	Patient expenditure form	x	x	x
Medical record				
Enrollment data (date of diagnosis, date of enrollment, date of ART)		x		
Appointment adherence		x	x	x
Pharmacy visit adherence		x	x	x
ART regimen		x	x	x
Laboratory				
Baseline laboratory test (creatinine, CD4, liver)		x		
Viral load		Per protocol above		

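### Patient expenditure is recorded at baseline in every arm, but the cost analysis specifies no adjustment for it, so the patient-cost comparison may be less precise than the data allow (minor)

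*Combined protocol and SAP*

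**What the plan says.** The cost part of Data analysis has two sentences. The first is directional: "We hypothesize that the intervention arms will result in reduced patient-level and health-center costs". The second lists two outcomes. One is a cost figure for each arm: "Outcomes will include: (a) annual cost per patient in each cohort/arm (per patient year cost". The other weighs cost against benefit and is given as "b) cost-effectiveness of the intervention arms compared with usual care". No regression, covariate, standard error or confidence interval is named for either. The generalized estimating equations in the same section are written for viral suppression and adherence.

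Main outcome variables describes "patient-level costs borne by patient or relatives of the patient towards their care (i.e. transportation to clinic, missed days of work". Table 2 has a row for "Patient costs/expenditures", source "Patient expenditure form", marked at baseline, 6 months and 12 months. Research visits applies this to every arm: "All participants will have research visits at baseline (study enrollment, which will occur in the first month after enrollment".

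Clinical visits gives all three arms monthly pick-ups and three-monthly clinic visits up to month 6, and spacing starts only then. Randomization is stratified by age and clinic. The only stated use of baseline covariates is the between-arm comparison under Assessment of randomization, and no adjustment follows from it.

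**The concern.** Transport and lost work depend largely on where a person lives and what they earn. Both plausibly persist over a year, so baseline expenditure may predict later patient cost. It is recorded before spacing can affect it, which makes it a legitimate covariate.

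If it is left out, the predictable part of the between-patient spread stays in the error term. With 30 per arm, a few patients with long journeys or high earnings can fall into one arm by chance. That imbalance carries into the cost difference in either direction. The pilot is meant to supply effect sizes for a larger study, so the width of the interval for patient cost matters even without a formal test.

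**Working it through.** The plan gives no cost SD, cost difference, alpha, power or dropout for this outcome, so there is no stated figure to reproduce.

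**Inputs from the documents:** 30 per arm (Overview and Specific Aims); patient expenditure at baseline, 6 and 12 months (Table 2); the visit schedules (Clinical visits).

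**Assumptions:** baseline-to-follow-up correlation r of 0.3 to 0.7; two-sided 5%; no dropout.

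**Step 1. Precision of one early arm against usual care, in SD units of cost.**

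Unadjusted SE = sqrt(2/30) = 0.258. The 95% half-width is 1.96 x 0.258 = 0.506. The difference detectable with 80% power is (1.96 + 0.842) x 0.258 = 0.723.

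Adjusted SE = 0.258 x sqrt(1 - r^2). The variance is cut by r^2, and 1 - r^2 is what remains.

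| r | Variance cut | Half-width | Detectable at 80% | Equivalent n per arm, 30/(1 - r^2) | Power for 0.5 SD |
|---|---|---|---|---|---|
| none | - | 0.506 | 0.723 | 30 | 49% |
| 0.3 | 9% | 0.483 | 0.690 | 33 | 53% |
| 0.5 | 25% | 0.438 | 0.626 | 40 | 61% |
| 0.7 | 49% | 0.361 | 0.517 | 59 | 77% |

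**Step 2. Chance imbalance.** The probability that baseline means differ by more than 0.25 SD in either direction is 2 x (1 - Phi(0.25/0.258)) = 33% per comparison.

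In 20,000 simulated three-arm trials with normal costs and no true difference, overall type I error was 5.0% to 5.1% unadjusted and 4.8% to 5.2% adjusted. Neither analysis is biased. Among the 17% of trials with an imbalance of at least 0.25 SD favouring the early arm:

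| r | Mean spurious saving, unadjusted | Significant false saving, unadjusted |
|---|---|---|
| 0.3 | 0.12 SD | 5.7% |
| 0.5 | 0.20 SD | 9.3% |
| 0.7 | 0.27 SD | 12.3% |

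With adjustment, the false-saving rate in these trials was 2.5% to 2.8%. The opposite imbalance hides a saving by symmetry.

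**Step 3. A cost model tied to the schedule.** Pick-ups after month 0 number 12 in usual care. After advancing they number 8: months 1 to 6, then 9 and 12. Assumed: 90% advance; per-trip cost is lognormal with CV 0.5, 0.7 or 1.0; annual cost is per-trip cost times trips; rho is set on the log scale. Each setting used 4,000 trials of 30 v 30 with HC3 standard errors. Power, unadjusted to adjusted:

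| CV | rho 0.5 | rho 0.7 |
|---|---|---|
| 0.5 | 76.0% to 83.6% | 76.3% to 93.1% |
| 0.7 | 48.1% to 55.2% | 47.7% to 69.3% |
| 1.0 | 28.7% to 32.6% | 28.8% to 41.5% |

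The gains are 7.6, 7.1 and 3.9 points at rho 0.5, and 16.8, 21.6 and 12.7 points at 0.7. At rho 0.3 the change is about 1 point or less. At rho 0 adjustment loses 1 to 2 points. A repeat run agreed to within simulation error.

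**Step 4. Scale of rho.** A log-scale rho is a smaller correlation on the cost scale: (exp(rho s^2) - 1)/(exp(s^2) - 1), with s^2 = ln(1 + CV^2) and the same CV at baseline. At rho 0.5 this gives 0.47, 0.45 and 0.41 for CV 0.5, 0.7 and 1.0. The variance cuts are then about 22%, 20% and 17%, not 25%.

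**The case against.** A reader might infer that the plan commits to a raw comparison of arm means. It does not: it names outcomes and is silent on method. What can be said is that no baseline adjustment is specified.

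A reader might also infer that the comparison is biased towards finding a saving. The arms are randomized, the unadjusted difference is unbiased, its type I error holds, and a valid confidence interval already allows for chance imbalance in either direction. The conditional rates in Step 2 describe unlucky trials, not the method's overall error rate.

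The randomization check could also reveal a marked imbalance in baseline expenditure. That is true, but nothing is planned to follow from it, and a covariate chosen after that look is a post-hoc choice.

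The correlation may be low. Baseline falls in the first month for newly diagnosed patients, and the form's recall period is not stated, so early spending may be a poor guide to later routine trips. The Step 3 model also makes annual cost exactly trips times per-trip cost, with no other variation, which is favourable to adjustment. Both limits stand.

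Two further objections stand. The pilot states no test or power for cost and admits limited power, so the power figures are only a yardstick for precision. The cost section also lacks any uncertainty method and any effectiveness measure for the cost-effectiveness outcome, and those gaps come before the choice of covariate.

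**Conclusion.** The point holds as a minor refinement. A baseline measure of patient cost is collected in all arms before the schedules separate, and the planned cost analysis gives it no role beyond a balance check. What is at stake is precision and protection against chance imbalance in either direction. Validity is not in question.

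The size rests on a correlation and a cost spread that the documents do not give. The benefit is negligible at a correlation of about 0.3, useful at 0.5, substantial at 0.7, and slightly negative at zero. The conclusion covers patient-level cost only. For facilities the plan says "To ascertain the cost to the health facility, we will estimate fixed (i.e. equipment, human resources) and variable" costs, and no baseline measurement of these is described.

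**What to change.** Add to the cost analysis in Data analysis, for example: *The difference in mean annual patient-level cost between each early arm and usual care will be estimated by linear regression on arm, baseline patient expenditure, age stratum and clinic, with a robust or bootstrap 95% CI. The adjusted difference will be used for the patient-cost part of the cost-effectiveness analysis. Unadjusted arm means will also be shown.*

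Also state whether expenditure reported at baseline counts toward annual cost. If it is simply added to the outcome, the adjusted arm difference does not change, because only the coefficient on baseline rises by one. The arm means and the unadjusted difference do change, so the definition should be fixed in advance.

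The cost is a few lines of text and a handful of model terms: one for baseline expenditure, one for age, and up to three for clinic, since Study setting names four sites. No new data or visits are needed. If baseline expenditure predicts nothing, about 1 to 2 points of power are lost to that covariate. The simulations did not include the age and clinic terms.
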